# 8.1.8.3 Timing for Administration of Pembrolizumab

For those subjects enrolled in Arm 2 (MK-1088 and pembrolizumab), study treatment with pembrolizumab should be administered on Day 1 of each cycle after all procedures/assessments have been completed as detailed in the SoA (Section 1.3). All study treatments of pembrolizumab will be administered on an outpatient basis. Study treatment of pembrolizumab may be administered up to 3 days before or after the scheduled Day 1 of each cycle due to administrative reasons except for C1D1, where the window is +3 days from allocation.

Please refer to the Pharmacy Manual for specific instructions regarding preparation of the pembrolizumab infusion fluid, and administration.

### 8.1.9 Discontinuation and Withdrawal

Participants who discontinue study intervention before completion of the treatment period should be encouraged to continue to be followed for all remaining study visits as outlined in the SoA (Section 1.3) and Section 8.11.3.

Participants who withdraw from the study should be encouraged to complete all applicable activities scheduled for the final study visit at the time of withdrawal. Any AEs that are present at the time of withdrawal should be followed in accordance with the safety requirements outlined in Section 8.4.

# 8.1.9.1 Withdrawal From Future Biomedical Research

Participants may withdraw their consent for FBR. Participants may withdraw consent at any time by contacting the study investigator. If medical records for the study are still available, the investigator will contact the Sponsor using the designated mailbox ([contact]). Subsequently, the participant's consent for FBR will be withdrawn. A letter will be sent from the Sponsor to the investigator confirming the withdrawal. It is the responsibility of the investigator to inform the participant of completion of withdrawal. Any analyses in progress at the time of request for withdrawal or

PROTOCOL/AMENDMENT NO.: 002-01

already performed before the request being received by the Sponsor will continue to be used as part of the overall research study data and results. No new analyses would be generated after the request is received.

If the medical records for the study are no longer available (eg, if the investigator is no longer required by regulatory authorities to retain the study records) or the specimens have been completely anonymized, there will no longer be a link between the participant's personal information and their specimens. In this situation, the request for specimen withdrawal cannot be processed.

# 8.1.10 Participant Blinding/Unblinding

This is an open-label study; there is no blinding for this study. The emergency unblinding call center will be available so that a health care provider can obtain information about study intervention in emergency situations where the investigator is not available.

## 8.1.11 Calibration of Equipment

The investigator or qualified designee has the responsibility to ensure that any device or instrument used for a clinical evaluation/test during a clinical study that provides information about inclusion/exclusion criteria and/or safety or efficacy parameters shall be suitably calibrated and/or maintained to ensure that the data obtained are reliable and/or reproducible. Documentation of equipment calibration must be retained as source documentation at the study site.

# 8.2 Efficacy/Immunogenicity Assessments

## 8.2.1 Tumor Scans and Assessment of Disease

Throughout this section, the term 'scan' refers to any medical imaging data used to assess tumor burden and may include cross-sectional imaging (such as CT or MRI), medical photography, bone imaging, or other methods as specified in this protocol.

In addition to survival, efficacy will be assessed based on evaluation of scan changes in tumor burden over time, until the participant is discontinued from the study or goes into survival follow-up. The process for scan collection and retention and/or transfer can be found in the SIM.

Tumor scans by CT are strongly preferred. For the abdomen and pelvis, contrast-enhanced MRI may be used when CT with iodinated contrast is contraindicated, or when mandated by local practice. The same imaging technique should be used in a participant throughout the study to optimize the reproducibility of the assessment of existing and new tumor burden and improve the accuracy of the response assessment based on scans.

Note: For the purposes of assessing tumor scans, the term "investigator" refers to the local investigator at the site and/or the radiological reviewer at the site or at an offsite facility.

PROTOCOL/AMENDMENT NO.: 002-01

Brain imaging is required at screening for participants with a history of brain metastases or when clinically indicated and on-study when clinically indicated or to confirm CR when brain metastases were present at screening.

• If brain scans are performed, magnetic resonance imaging is preferred; however, CT imaging will be acceptable, if MRI is medically contraindicated.

### **Prostate Cancer**

Bone scintigraphy (eg, nuclear medicine bone scan, Tc99 bone scan, bone scan, etc.) of the whole body is required for all participates at screening and on-study for all scheduled imaging visits and to confirm PCWG-modified RECIST 1.1 bone PD.

• Other bone imaging modalities (eg, FDG-PET, PET, PSMA PET, MRI, SPECT, etc.) cannot be a substitute for the bone scan (see Appendix 9, Section 10.9).

### **Non-Prostate Cancer**

Bone imaging (e.g. bone scan, PET scan, etc.) should be performed to evaluate bone metastases when clinically indicated at screening and on-study or to confirm CR when bone metastases were present at screening.

### 8.2.2 Initial Tumor Scans

Initial tumor scans at screening must be performed within 28 days before the date of allocation. Any scans obtained after Cycle 1 Day 1 cannot be included in the screening assessment. The investigator must review screening scans to confirm the participant has measurable disease per RECIST 1.1, for mCRPC participants by PCWG-modified RECIST 1.1.

If brain scans are required to document the stability of existing metastases, the brain scan should be acquired during screening. The specific methods permitted for this study are described in the SIM.

Bone scintigraphy (eg, Tc99 bone scan, etc.) is required for all participants with prostate cancer. For all other participants, bone imaging (eg, bone scan, PET scan, etc.) is required only when clinically symptomatic (eg, with new bone pain, etc.).

## 8.2.3 Tumor Scans During the Study

The first on-study scan should be performed at 9 weeks (63 days  $\pm 7$  days) from the C1D1 date. Subsequent tumor scans should be performed every 9 weeks (63 days  $\pm 7$  days) or more frequently if clinically indicated. After 54 weeks (378 days  $\pm 7$  days), participants who remain on treatment will have scans performed every 12 weeks (84 days  $\pm 7$  days). Scan timing should follow calendar days and should not be adjusted for delays in cycle starts.

Scans are to be performed until disease progression is identified by the investigator, withdrawal of consent, pregnancy, or death, whichever occurs first.

Objective response should be confirmed by a repeat scan performed at least 4 weeks after the first indication of a response is observed. Participants will then return to the regular scan schedule, starting with the next scheduled time point. Participants who receive additional scans for confirmation do not need to undergo the next scheduled scan if it is fewer than 4 weeks later; scans may resume at the subsequent scheduled time point.

For non-prostate cancer participants, on-study brain or bone scans should be performed if clinically indicated or to confirm CR (if other lesions indicate CR and brain or bone lesions existed at screening).

For prostate cancer participants, radiographic progression will be determined according to PCWG-modified RECIST 1.1. Disease progression in bone lesions should be confirmed by another bone scan  $\geq 6$  weeks after site assessed first radiographic evidence of bone disease progression.

# 8.2.4 End of Treatment and Follow-up Tumor Scans

If participants discontinue study intervention, tumor scans should be performed at the time of discontinuation ( $\pm 4$  week window) unless previous scans were obtained within 4 weeks of discontinuation. If participants discontinue study intervention due to documented disease progression, this is the final required tumor scan.

If participants discontinue study intervention without documented disease progression, every effort is to be made to monitor disease status by acquiring tumor scans using the same schedule calculated from the date of allocation, refer to Section 8.2.3.

Scans are to be continued until one of the following conditions are met:

- Disease progression as defined by RECIST 1.1 or PCWG-modified RECIST 1.1
- The start of a new anticancer treatment.
- Pregnancy
- Death
- Withdrawal of consent
- The end of the study

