Part 1 Arm 1 and Arm 2: MK-1088 Administration/Dispense		X				X				X			X		MK-1088: taken orally QD from D1 through D21 of each treatment cycle.
Part 1 Arm 2: Pembrolizumab Administration		X				X				X			X		Pembrolizumab: administered IV Q3W on D1 of each treatment cycle.
Anticancer Therapy Status														X	Any changes in new treatment will be collected.
Disease Status														X	
Clinical Procedures/Assessme	nts														
Full Physical Examination	X													X	
Directed Physical Examination		X		X	X	X				X			X		
Height	X														
Weight	X	X				X				X				X	
Vital Signs	X	X	X	X	X	X	X	X	X	X	X	X	X	X	Obtain heart rate, respiratory rate, blood pressure, temperature.
12-lead Electrocardiogram	X	X	X			X	X								C1D1 and C2D1: Obtain predose and 2 hrs postdose. C1D2 and C2D2: Obtain predose.

Study Phase	Screening Phase a	Treatment Phase (3-Week Cycles)											End of Treatment	Notes	
Treatment Cycle/Title:	Screening (Visit 1)		Сус	le 1			Су	cle 2		(	Cycle :	3	Cycles 4 to 35	/Discon- tinuation	Notes
Treatment Days per Cycle:	Up to 28 days before Day 1 Cycle 1	Day 1 b	Day 2°	Day 8	Day 15	Day 1	Day 2°	Day 8	Day 15	Day 1	Day 8	Day 15	Day 1	At time of treatment discontinuation	Treatment Phase: Procedures, assessments, and samples are collected predose unless otherwise specified .
Scheduling Window (Days)	-28 to -1	0	0	±3	±3	±3	±3	±3	±3	±3	±3	±3	±3	+3	
ECOG Performance Status	X	X	x									X	Obtain within 72 hrs before the first dose of study intervention on D1 of each cycle.		
AE Monitoring	X	+											→	X	
Tumor Imaging Response Assessment (PCWG-modified RECIST 1.1 for prostate cancer participants; RECIST 1.1 for all other participants)	X	4 -	4										X	Treatment phase schedule:  Obtain every 9 weeks (±7 days)  After 54 weeks, obtain every 12 weeks (±7 days)	
Prostate cancer participants only: Bone Scan	X	4						·				Х	Tc99 bone scintigraphy (nuclear medicine bone scan) is required at screening and on-study at all protocol-required tumor assessment visits and when clinically indicated.  Tumor assessments visits:  Obtain every 9 weeks (±7 days)  After 54 weeks, obtain every 12 weeks (±7 days)		

Study Phase	Screening Phase a		Treatment Phase (3-Week Cycles)									End of Treatment	Notes		
Treatment Cycle/Title:	Screening (Visit 1)		Cycle 1 Cycle 2 Cycle 3 Cycles 4 to 35								/Discon- tinuation	Notes			

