# 1.3.1.2 Part 1, Arms 1 and 2, and Arm 1 Crossover to Arm 2: Posttreatment Phase

Table 2 Schedule of Activities: Posttreatment Phase for Part 1, Arm 1 and Arm 2, and Arm 1 Crossover to Arm 2

Study Phase:		Posttrea	tment		
Title:	Safe Follo		Imaging Follow-up	Survival Follow-up	Notes
Timing/frequency for Follow-up:	30 days after the last dose of study medication	Arm 2 only: 90 days after the last dose of pembrolizumab	Every 12 weeks	Every 12 weeks	
Scheduling Window (Days):	±7	±7	±7	±7	
Administrative Procedures					
Concomitant Medication Review	X	X			Arm 2: 90-day follow-up can be performed with a telephone call.
Anticancer Therapy Status	X			X	Any changes in new treatment will be collected.
Disease Status	X		X	X	See Sections 8.11.4.2 and 8.11.4.3.
Clinical Procedures / Assessments					
Full Physical Examination	X				
Vital Signs	X				Obtain heart rate, respiratory rate, blood pressure, temperature.
ECOG Performance Status	X				
AE Reporting	4		·		Arm 2: 90-day follow-up can be performed with a telephone call.
Vital Status	4			·	On Sponsor notification, all participants who do not/will not have a scheduled study visit or study contact during the Sponsor-defined time period will be contacted for their vital status.
Tumor Imaging Response Assessment			X		PCWG-modified RECIST 1.1 for prostate cancer participants; RECIST 1.1 for all other participants. Use the same type of scans obtained during treatment phase.
Laboratory Procedures / Assessments					
Comprehensive Chemistry Panel	X				
Hematology	X				
Thyroid Function Tests (TSH, T3 or free T3, free T4)	X				
Pharmacokinetics					
Plasma for MK-1088 PK	X				

AE=adverse event; ECOG=Eastern Cooperative Oncology Group; PCWG=Prostate Cancer Working Group; PK=pharmacokinetic; RECIST= Response Evaluation Criteria In Solid Tumors; TSH=thyroid-stimulating hormone.

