# 8.1.8 Study Intervention Administration

Study intervention should begin within 3 days of treatment allocation.

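### Table 2 and Section 8.2.4 set different scan calendars for participants who stop treatment without progression, so exploratory PFS and DOR timing depends on which one a site follows

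*Combined protocol and SAP*

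**What the plan says.** Four places describe imaging for a participant who is off treatment without progression.

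- **Section 8.2.4** says "every effort is to be made to monitor disease status by acquiring tumor scans using the same schedule calculated from the date of allocation" and refers to Section 8.2.3.
- **Section 8.2.3** places the first on-study scan 9 weeks "from the C1D1 date", then states "Subsequent tumor scans should be performed every 9 weeks". After week 54, "participants who remain on treatment will have scans performed every 12 weeks". It adds: "Scan timing should follow calendar days and should not be adjusted for delays in cycle starts". Table 1 carries the same 9-week interval and the same switch at week 54 for the treatment phase.
- **Table 2 (Section 1.3.1.2)**, Imaging Follow-up column, reads "Every 12 weeks" with a ±7-day window. It has no week-54 condition and does not say from which date the 12 weeks run.
- **Section 8.11.4.2** refers only to the schedule defined by the protocol, without an interval, and sends disease-status follow-up to Section 8.11.4.3, which covers the 12-weekly survival contacts.

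Section 3 ends PFS at the first documented progression or death, and DOR at progression or death. Both are exploratory, and Section 9.1 leaves their analysis to a separate sSAP.

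**The concern.** The same participant has two sets of due dates. Someone who stops for toxicity at week 9, without progression, is next due at week 18 under Section 8.2.4. Under Table 2 the next scan falls at week 21, if the clock starts at the end-of-treatment scan.

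Sites have reason to use the table. Section 4.1 sends them to Tables 1 and 2 for timing and windows, Section 7.1 asks discontinued participants to complete the procedures in the schedule of activities, and Section 8 makes adherence to that schedule mandatory. The disease-status note in Table 2 leads to Sections 8.11.4.2 and 8.11.4.3, not to Section 8.2.4.

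Progression is dated when it is documented, so scan spacing enters PFS and DOR directly. If Table 2 is followed, spacing before week 54 is 9 weeks on treatment and 12 weeks off it. Observed PFS and DOR would then depend partly on treatment status and on the section a site happened to use.

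**Working it through.** The plan states no figure for detection delay, so there is none to reproduce. Its day conversions are consistent: 9 × 7 = 63, 12 × 7 = 84, 54 × 7 = 378, and week 54 is the sixth 9-week scan.

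**Step 1. Due dates.** Inputs from the documents: 9-weekly to week 54 then 12-weekly (Section 8.2.3, Table 1), and 12-weekly (Table 2). Assumptions: the Table 2 clock starts at the end-of-treatment scan, and the week-54 switch also applies off treatment.

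| Stop at week | Sections 8.2.3/8.2.4, through week 66 | Table 2, through week 66 |
|---|---|---|
| 9 | 18, 27, 36, 45, 54, 66 | 21, 33, 45, 57 |
| 18 | 27, 36, 45, 54, 66 | 30, 42, 54, 66 |
| 27 | 36, 45, 54, 66 | 39, 51, 63 |

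**Step 2. Half-interval arithmetic.** If progression is uniform within a scan interval, mean delay = interval / 2. That gives 9/2 = 4.5 weeks and 12/2 = 6 weeks, a difference of 1.5 weeks.

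**Step 3. Individual shifts, stop at week 9.** Shift = Table 2 detection week minus Section 8.2.4 detection week.

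| True progression in weeks | Section 8.2.4 | Table 2 | Shift |
|---|---|---|---|
| 9–18 | 18 | 21 | +3 |
| 18–21 | 27 | 21 | −6 |
| 21–27 | 27 | 33 | +6 |
| 27–33 | 36 | 33 | −3 |
| 33–36 | 36 | 45 | +9 |
| 36–45 | 45 | 45 | 0 |

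Weighting by the width of each row: (9×3 − 3×6 + 6×6 − 6×3 + 3×9 + 9×0) / 36 = 54/36 = 1.5 weeks, as in step 2. The mean is positive, but individual shifts over this span run from 6 weeks earlier to 9 weeks later.

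**Step 4. Non-uniform progression.** Assumptions not in the documents: exponential time to progression after stopping, with median 8 to 52 weeks, and stopping at week 9, 18 or 27 (400,000 simulated times per row). Mean delay in weeks from true progression to the next scan:

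| Stop week | Median after stopping | 8.2.3 calendar | Table 2 | Difference |
|---|---|---|---|---|
| 9 | 8 | 5.11 | 7.02 | 1.91 |
| 9 | 26 | 5.18 | 6.32 | 1.14 |
| 9 | 52 | 5.46 | 6.16 | 0.70 |
| 18 | 8 | 5.17 | 7.02 | 1.85 |
| 18 | 52 | 5.56 | 6.15 | 0.59 |
| 27 | 8 | 5.27 | 7.02 | 1.75 |
| 27 | 52 | 5.69 | 6.16 | 0.47 |

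The rows not shown lie within these, so the range is about 0.5 to 1.9 weeks. The difference shrinks with slower progression because more events fall after week 54, where both calendars are 12-weekly. If Section 8.2.3 is read literally, so that off-treatment participants stay 9-weekly after week 54, the range is about 1.6 to 1.95 weeks.

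**Step 5. Anchor date.** Section 8.2.3 counts from C1D1 and Section 8.2.4 from allocation. Section 8.1.8 says "Study intervention should begin within 3 days of treatment allocation", so the two differ by at most 3 days, inside the ±7-day window.

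**The case against.** The strongest reply is that little rests on this. PFS and DOR are exploratory, allocation is nonrandom, and Section 9.8 says no hypothesis testing will be done. Dose-finding decisions follow DLT counts in Cycle 1. The affected group is narrow: off treatment, without progression, without new anticancer therapy (which ends scanning), and mainly before week 54. Section 8.2.4 also requires a scan at discontinuation, within a ±4-week window, which can find progression off either grid. All of this stands, and it makes the point minor.

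It can also be said that a site following Section 8.2.4 before week 54 scans at the same interval on and off treatment. That is correct: the later detection arises only where Table 2 is followed.

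It does not help to read Table 2 as applying only after week 54. Table 1 writes out the week-54 switch and Table 2 does not. Section 8.11.4.2 does not settle the matter, since it gives no interval and points to the survival contacts.

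A reader might infer that dose levels with more toxicity-related stopping will look better on PFS or DOR. The direction is plausible if Table 2 is followed, but the documents give no count of participants who would stop without progression, by dose or overall, and the sSAP that will define censoring is not available. An average of about 1.5 weeks in an unknown fraction of participants is not shown to change how any dose level looks.

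**Conclusion.** The inconsistency is real and stands in the current text. For participants who stop without progression, mainly before week 54, Table 2 and Section 8.2.4 give different scan dates. The off-treatment interval after week 54 is also left open.

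If Table 2 is followed, mean detection is later by 1.5 weeks under uniform progression, or by about 0.5 to 1.9 weeks under the stopping and progression times assumed above, with the Table 2 clock starting at the end-of-treatment scan. A reader might take the 3-week difference between the intervals as the largest possible shift. It is not: in the week-9 example, shifts run from 6 weeks earlier to 9 weeks later. The anchor mismatch is negligible in size.

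The effect is confined to exploratory PFS and DOR. DLTs, dose finding and the planned sample size of about 80 do not depend on it, and confirmed ORR is little affected. Any difference between dose levels cannot be derived from the documents.

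**What to change.** Reconcile Table 2 and Sections 8.2.3, 8.2.4 and 8.11.4.2 to one imaging calendar and one anchor date. State the off-treatment interval explicitly, both before and after week 54, and have Section 8.11.4.2 refer to the imaging section rather than to the survival contacts. Using the same calendar on and off treatment, as Section 8.2.4 indicates, removes the dependence of PFS and DOR timing on treatment status.

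Changing the Table 2 cell alone would not be enough, because the wording about participants who remain on treatment and the two anchor dates would still be there. The cost is a few words in each place, and an amendment is already needed before Part 2. If the 9-week interval is kept off treatment, the step 1 calendars imply two extra scans through week 54 for a stop at week 9 (five against three) and one for a stop at week 18 (four against three) or week 27 (three against two).

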## 8.2.5 RECIST 1.1 and PCWG-modified RECIST 1.1 Assessment of Disease

For participants other than those with prostate cancer, RECIST 1.1 will be used as the primary measure for assessment of tumor response, date of disease progression, and as a basis for all protocol guidelines related to disease status (eg, discontinuation of study intervention). Although RECIST 1.1 references a maximum of 5 target lesions in total and 2

per organ, this protocol allows a maximum of 10 target lesions in total and 5 per organ, if clinically relevant to enable a broader sampling of tumor burden.

For participants with prostate cancer, the primary measure for assessment of tumor response, date of disease progression and as the basis for all protocol guidelines related to disease status (eg, discontinuation of study intervention) will be PCWG-modified RECIST 1.1. Assessment of treatment response in the soft tissue will be according to RECIST 1.1, modified as above. Assessment of treatment response in the bone will be according to the rules of PCWG as described in Appendix 9.

Soft tissue response and bone response assessments will be combined to produce an overall radiographic response, as shown in Table 10.

Table 10 Overall Radiographic Response per PCWG-modified RECIST 1.1

Soft Tissue Response	Bone Scan Result	PCWG-modified RECIST 1.1 Time Point Response Entered into CRF
PD	Any	PD
Any	PD	PD
Any (except PD)	PDu	PDu
NE	Non-PD, NED or NE	NE
NED	NE	NE
NED	Non-PD	Non-CR/Non-PD
NED	NED	NED
SD	Non-PD, NED, or NE a	SD
Non-CR/Non-PD	Non-PD, NED, or NE a	Non-CR/Non-PD
PR	Non-PD, NED or NE*	PR
CR	Non-PD or NE*	PR (if target lesions were present at screening)  Non-CR/Non-PD (if no target lesions at screening)
CR	NED	CR

Abbreviations: CR = complete response; CRF = case report form; NE = nonevaluable; NED = no evidence of disease; PCWG = Prostate Cancer Working Group; PD = progressive disease; PDu = progressive disease unconfirmed; PR= partial response; RECIST 1.1 = Response Evaluation Criteria in Solid Tumors Version 1.1; SD = Stable disease.

<sup>a If the bone scan is entirely missing or was not conducted, and bone lesions were present at screening, then the overall response is NE.

PROTOCOL/AMENDMENT NO.: 002-01

For all participants (prostate cancer and non-prostate cancer), if disease progression is established by the investigator, the process continues as follows:

- Investigator judgment will determine action
- If the participant is clinically stable and study intervention is to continue, communication with the Sponsor is required and a reconsent addendum must be signed
- Obtain scans per original protocol schedule

For the purpose of this decision process, lack of clinical stability is defined as:

- Unacceptable toxicity
- Clinical signs or symptoms indicating clinically significant disease progression
- Decline in performance status
- Rapid disease progression or threat to vital organs or critical anatomical sites (eg, CNS metastasis, respiratory failure due to tumor compression, spinal cord compression) requiring urgent alternative medical intervention

